12.8.2. ECG

ECG Parameter	Units	Clinical Concern Range	
		Lower	Upper
Absolute			
Absolute QTc Interval	msec		>500
Absolute PR Interval	msec	<110	>220
Absolute QRS Interval	msec	<75	>110
Change from Baseline			

ECG Parameter	Units	Clinical Concern Range	
		Lower	Upper
Increase from Baseline QTc	msec		>60

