#### **8.1.2. QTc Stopping Criteria**

The QTc should be based on single or averaged QTc values of triplicate electrocardiograms obtained over a brief (e.g., 5-10 minute) recording period.

A participant who meets either bulleted criterion below will be withdrawn from study:

- QTcF >500 msec
- Change from baseline of QTc >60 msec

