12.11.7. Safety Tables

Safety: Tables					
No.	Population	IDSL / Example Shell	Title	Programming Notes	Deliverable [Priority]
Adverse Events (AEs)					
3.1.	All Subjects	AE1	Summary of All Adverse Events by System Organ Class and Preferred Term	ICH E3	SAC [1]
3.2.	All Subjects	AE1	Summary All Drug-Related Adverse Events by System Organ Class and Preferred Term/by Overall Frequency	ICH E3	SAC [1]
Serious and Other Significant Adverse Events					
3.3.	All Subjects	AE16	Summary of Serious Adverse Events by System Organ Class and Preferred Term (Number of Participants and Occurrences)	FDAAA, EudraCT	SAC [1]
3.4.	All Subjects	AE1	Summary of Adverse Events Leading to Permanent Discontinuation of Study Treatment or Withdrawal from Study by System Organ Class and Preferred Term	IDSL	SAC [1]
Laboratory: Chemistry					
3.5.	All Subjects	LB1	Summary of Chemistry Changes from Baseline	ICH E3	SAC [1]
Laboratory: Haematology					
3.6.	All Subjects	LB1	Summary of Haematology Changes from Baseline	ICH E3	SAC [1]
Laboratory: Urinalysis					
3.7.	All Subjects	LB1	Summary of Urine Concentration Changes from Baseline	ICH E3	SAC [1]
3.8.	All Subjects	UR3	Summary of Urinalysis Dipstick Results	ICH E3	SAC [1]
Laboratory: Hepatobiliary (Liver)					
3.9.	All Subjects	LIVER1	Summary of Liver Monitoring/Stopping Event Reporting	IDSL	SAC [1]

Safety: Tables					
No.	Population	IDSL / Example Shell	Title	Programming Notes	Deliverable [Priority]
ECG					
3.10.	All Subjects	EG1	Summary of ECG Findings	IDSL	SAC [1]
3.11.	All Subjects	EG2	Summary of Change from Baseline in ECG Values by Visit	IDSL	SAC [1]
3.12.	All Subjects	SAFE_T4	Summary of Number of Participants with Maximum ECG Values Meeting or Exceeding Pre-Specified Ranges of Concern by Category, Treatment and Timepoint.		SAC [1]
Vital Signs					
3.13.	All Subjects	VS1	Summary of Change from Baseline in Vital Signs	ICH E3 Include body temperature, heart rate, blood pressure.	SAC [1]
Columbia Suicide Severity Rating Scale (C-SSRS)					
3.14.	All Subjects	CSSRS1 (SAFE_T1)	Summary of C-SSRS Suicidal Ideation or Behaviour	Include Placebo column.	SAC [1]
Laboratory: Other					
3.15.	All Subjects	SAFE_T2	Summary of Faecal Occult Blood Test (FOBT) Data		SAC [1]
3.16.	All Subjects	LB1	Summary of Cardiac Troponin (cTn) Changes from Baseline		SAC [1]
3.17.	All Subjects	LB1	Summary of Coagulation Profile Changes from Baseline		SAC [1]
Spirometry					
3.18.	All Subjects	SAFE_T3	Summary of Spirometry Data		SAC [1]

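### The SAP's QTc flag limits equal the protocol's withdrawal limits with no tier below them, so no specified ECG display counts participants with moderate QTc rises (unless the unseen shell SAFE_T4 does)

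*SAP*

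**What the plan says.** SAP 12.8.2 lists the ECG limits of potential clinical importance. For QTc there are two, both upper limits: "Absolute QTc Interval" above 500 msec and "Increase from Baseline QTc" above 60 msec. The same table sets limits for "Absolute PR Interval" (below 110 or above 220 msec) and "Absolute QRS Interval" (below 75 or above 110 msec).

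Protocol 8.1.2 gives the withdrawal criteria as "QTcF >500 msec" and "Change from baseline of QTc >60 msec", with the consequence that "A participant who meets either bulleted criterion below will be withdrawn from study". Protocol 6.2 excludes anyone with QTcF above 450 msec at entry.

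The displays that use such limits are Table 3.12 ("Summary of Number of Participants with Maximum ECG Values Meeting or Exceeding Pre-Specified Ranges of Concern by Category, Treatment and Timepoint", shell SAFE_T4), Listing 27 (all ECG values of any participant with a flagged value) and Listing 28 (the flagged values). The other ECG displays are Table 3.10 and Listings 29-30 (ECG findings) and Table 3.11 (change from baseline by visit). ECG is a named secondary safety endpoint. The scheduled post-dose ECGs are single recordings at 30 h and at the Day 8 visit.

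**The concern.** A flag limit is most useful when it picks up participants who have moved noticeably but have not reached the point at which the protocol already acts. Here the QTc flag and the QTc action sit at the same values, so the flag says little that the withdrawal record does not.

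Other parts of the same SAP appendix work differently. Liver tests are flagged at ALT of at least 2xULN and bilirubin of at least 1.5xULN (12.8.1), below the 3xULN and 2xULN in protocol Appendix 6. Vital-sign changes have two tiers (12.8.3): systolic pressure 20 and 40 mmHg, diastolic 10 and 20 mmHg, heart rate 15 and 30 bpm.

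With at most about 30 participants per arm, the by-arm QTc counts are very likely to be zero in both arms even if some participants have moderate rises. A reader could take those zeros as evidence that no individual had a QTc change of note.

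**Working it through.** The plan gives no operating figure for these flags, so there is none to reproduce. The check has three parts.

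**1. Side-by-side comparison**

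| Rule | Absolute QTc | Change from baseline |
|---|---|---|
| SAP 12.8.2 flag | >500 msec | >60 msec |
| Protocol 8.1.2 withdrawal | >500 msec (QTcF) | >60 msec |

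If the SAP's QTc is QTcF, the two rules agree for every pair of baseline and on-study values.

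**2. What goes unflagged**

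The largest QTc that raises no flag is min(500, baseline + 60):
- baseline 400: 460 msec
- baseline 420: 480 msec
- baseline 440 to 450: 500 msec

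Example: a baseline of 445 is eligible (not above 450). A later value of 495 is a change of 495 - 445 = 50, which is not above 60, and 495 is not above 500. There is no QTc flag.

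**3. Size**

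These inputs are assumptions, not document figures: baseline B normal with mean 405 and SD 18, truncated at 450; change D normal with mean d and SD s = 10 or 15 msec; one post-dose reading; 30 participants per arm. For limits A (absolute) and C (change):

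- p = P(B + D > A or D > C), that is, the average over B of 1 - Phi((min(A - B, C) - d)/s)
- P(at least one flag among 30) = 1 - (1 - p)^30
- expected number flagged = 30p

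In the table, the first figure in each cell is for s = 10 and the second for s = 15. The current limits are A = 500, C = 60. The last two columns use A = 450, C = 30, so they count everyone in the added or the existing categories.

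| True mean rise d | Current: P(any) | With added tiers: P(any) | With added tiers: 30p |
|---|---|---|---|
| 0 msec | about 0; 0.1% | 29%; 70% | 0.3; 1.2 |
| 10 msec | about 0; 1.3% | 82%; 98% | 1.7; 3.7 |
| 20 msec | 0.1%; 11% | >99.9%; >99.9% | 6.6; 8.9 |

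Worked cell: for d = 20, s = 10 with added tiers, p = 0.219, so 30 x 0.219 = 6.6. For d = 0, s = 15, p = 0.0395, so 30 x 0.0395 = 1.2 and 1 - (1 - 0.0395)^30 = 70%.

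For comparison, Table 3.11 allows a between-arm difference in mean change with standard error s x sqrt(2/30), which is 2.6 to 3.9 msec. A 20 msec effect is 5.2 to 7.7 standard errors and a 10 msec effect 2.6 to 3.9.

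**The case against.** A reader might infer that these ECG displays can only repeat the QTc withdrawals and can never count a moderate change. The documents do not support that, for three reasons.

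- PR and QRS limits also drive the displays. A participant with QTc 410 to 420 but PR 225 is flagged, and Listing 27 then prints all of that participant's ECG values, QTc included.
- A QTc flag need not equal a withdrawal. Protocol 8.1.2 allows the decision to rest on averaged triplicate readings, and protocol 9.7.4 foresees additional QTc readings. Day 8 is the final visit, so a flag there leaves little to withdraw from.
- Table 3.12 is organised by category, and its shell SAFE_T4 is outside the supplied text. Finer QTc categories there can be neither confirmed nor excluded.

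These points limit the claim but leave its core. In the supplied SAP the only numeric ECG limits of concern are those in 12.8.2. If SAFE_T4 has finer categories, 12.8.2 should state them.

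Four further objections carry weight:

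- Table 3.11 would show a mean shift of the size considered here. It would not show how many participants moved, or how far.
- The added tiers flag people by chance: with no drug effect, the probability of at least one flag among 30 is 29-70%. A bare count in the active arm therefore says little without the placebo arm beside it.
- Matching a protocol action limit is not unique to QTc. Cardiac troponin is flagged at essentially the limit in protocol 8.1.3.1, and no document requires a lower tier.
- The protocol's risk table lists no QT-prolongation risk. The first scheduled post-dose ECG falls at 30 h, which is 18 h after the second dose, against a median Tmax of 1.5 h. No ECG display could recover an effect confined to peak concentrations.

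The last two points argue for treating this as a cheap improvement rather than a serious defect.

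**Conclusion.** The point holds as a reporting gap. The QTc limits in 12.8.2 coincide with the withdrawal limits and have no intermediate tier. The QTc flags in Listings 27-28, and in Table 3.12 unless SAFE_T4 is finer, add almost nothing to the withdrawal criteria. A rise from 445 to 495 msec is one example of what they miss.

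The loss is a per-participant count of moderate changes; an average shift would still be seen. Under the assumptions above, a true 20 msec rise would leave the current QTc counts empty with probability of about 89% to 99.9%, while the added categories would show about 7-9 participants against 0.3-1.2 expected by chance. At 10 msec the contrast is weaker: 1.7-3.7 against 0.3-1.2. These sizes depend on the assumed baseline distribution and SD of change. The coincidence of the limits does not, but it does require that the SAP's QTc is QTcF. The SAP does not say so in 12.8.2, and its abbreviation list contains both QTcF and QTcB.

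**What to change.** In SAP 12.8.2, keep the >500 and >60 msec rows, state that QTc means QTcF, and add two reporting categories:

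- QTcF >450 to 500 msec (450 is the protocol's own entry limit)
- increase from baseline >30 to 60 msec (half the existing change limit, the same ratio as the SAP's two-tier vital-sign changes)

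Carry both into Table 3.12, by arm and timepoint, and into Listings 27-28. If SAFE_T4 already contains such categories, bring 12.8.2 and the listings into line with it. Note with Table 3.12 that the intermediate counts are to be read against placebo.

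The protocol's withdrawal criteria stay as they are. The cost is a SAP wording change and two more rows per arm, with no new data. The downside is some flags from ordinary variation, about 0.3-1.2 participants per arm under the assumptions used here.

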12.8.3. Vital Signs

Vital Sign Parameter (Absolute)	Units	Clinical Concern Range	
		Lower	Upper
Systolic Blood Pressure	mmHg	<85	>160
Diastolic Blood Pressure	mmHg	<45	> 90
Heart Rate	bpm	<50	>110

Vital Sign Parameter (Change from Baseline)	Units	Clinical Concern Range			
		Decrease		Increase	
		Lower	Upper	Lower	Upper
Systolic Blood Pressure	mmHg	≥20	≥40	≥20	≥40
Diastolic Blood Pressure	mmHg	≥10	≥20	≥10	≥20
Heart Rate	bpm	≥15	≥30	≥15	≥30

12.9. Appendix 9: Pharmacokinetic / Pharmacodynamic Analyses

12.9.1. Pharmacokinetic / Pharmacodynamic Dataset Specification

Specification for PK-PD dataset [Proposed dataset name PKPD]

Variable short name	Assessment description	Format	Unit	Valid Values / Format
C	Data Identifier	Integer	-	0
ID	Unique subject number	Numeric		Different ID for different subject
STUD	Protocol Number	Integer	-	207464
SUBJ	Subject identifier in study	Integer	-	Maximum 10 characters (numeric or text). Different identifier for each subject
CENT	Study centre identifier	Integer	-	
DAY	Day of sampling	Integer	See footnotes	See footnotes
C2	Conc of GSK2798745 2 h post first dose	Decimal 3 d.p	ng/mL	Numeric – For placebo TRT arm C2 = 0
C26	Conc of GSK2798745 26 h post first dose	Decimal 3 d.p	ng/mL	Numeric - For placebo TRT arm C26 = 0
AUC26	Area under curve (0-26h)	Decimal 3 d.p	ng.h/mL	Numeric - For placebo TRT arm AUC26 = 0
Analyte	Drug analysed	Integer	-	GSK2798745
Base_PD	Baseline corrected BAL total protein (i.e. before LPS challenge and 2h post dose)	Decimal 3 d.p	-	BAL total protein
745_PD	Corrected BAL total protein at 26h post dosing with GSK2798745 (i.e. 24h post LPS challenge)	Decimal 3 d.p		BAL total protein
AGE	Age	Decimal	Yrs	Integer. Age in years at time of screening rounded down to give age at last birthday.
WT	Weight	Decimal	Kg	Weight in kilograms at time of screening.
BMI	Body mass index	Decimal	kg/m ²	Body mass index calculated as weight divided by height squared
SEX	Subject gender	Integer	-	Integer. One of the following - 1 = Male

12.10. Appendix 10: Abbreviations & Trade Marks

12.10.1. Abbreviations

Abbreviation	Description
ADaM	Analysis Data Model
AE	Adverse Event
ALT/SGPT	Alanine Amino Transferase / Serum Glutamic-Pyruvic Transaminase
AST/SGOT	Aspartate Amino Transferase / Serum Glutamic Oxaloacetic Transaminase
A&R	Analysis and Reporting
BAL	Bronchoalveolar Lavage
BUN	Blood Urea Nitrogen
CDISC	Clinical Data Interchange Standards Consortium
CI	Confidence Interval
CrI	Credible Interval
CPMS	Clinical Pharmacology Modelling & Simulation
CRP	C-reactive Protein
CS	Clinical Statistics
CSR	Clinical Study Report
CTR	Clinical Trial Register
CV _b / CV _w	Coefficient of Variation (Between) / Coefficient of Variation (Within)
DIC	Deviance Information Criterion
DBF	Database Freeze
DBR	Database Release
DOB	Date of Birth
DP	Decimal Places
eCRF	Electronic Case Record Form
EMA	European Medicines Agency
FDA	Food and Drug Administration
FDAAA	Food and Drug Administration Clinical Results Disclosure Requirements
GSK	GlaxoSmithKline
HPD	Highest Posterior Density
IA	Interim Analysis
ICH	International Conference on Harmonization
IDMC	Independent Data Monitoring Committee
IDSL	Integrated Data Standards Library
IL	Interleukin
IMMS	International Modules Management System
INR	International Normalisation Ratio
IP	Investigational Product
ITT	Intent-To-Treat
LLQ	Lower Limit of Quantification
LPS	Lipopolysaccharide
MCMC	Monte Carlo Markov Chain
MMRM	Mixed Model Repeated Measures

Abbreviation	Description
PCI	Potential Clinical Importance
PD	Pharmacodynamic
PDMP	Protocol Deviation Management Plan
PK	Pharmacokinetic
PP	Per Protocol
PP	Posterior Probability
PopPK	Population PK
PTT	Prothrombin Time
QC	Quality Control
QTcF	Fridericia's QT Interval Corrected for Heart Rate
QTcB	Bazett's QT Interval Corrected for Heart Rate
RAP	Reporting & Analysis Plan
RAMOS	Randomization & Medication Ordering System
SAC	Statistical Analysis Complete
SDSP	Study Data Standardization Plan
SDTM	Study Data Tabulation Model
SOP	Standard Operation Procedure
SP-B	Surfactant Protein B
TA	Therapeutic Area
TFL	Tables, Figures & Listings
TNF-alpha	Tumour Necrosis Factor alpha
ULQ	Upper Limit of Quantification
vWF	Von Willebrand Factor

12.10.2. Trademarks

Trademarks of the GlaxoSmithKline Group of Companies
HARP
RANDALL NG

Trademarks not owned by the GlaxoSmithKline Group of Companies
NONMEM
R
SAS
WinNonlin

12.11. Appendix 11: List of Data Displays

12.11.1. Data Display Numbering

The following numbering will be applied for RAP generated displays:

Section	Tables	Figures
Study Population	1.1 to 1.13	
Pharmacodynamic and Biomarker	2.1 to 2.17	2.1 to 2.29
Safety	3.1 to 3.18	
Pharmacokinetic	4.1 to 4.8	4.1 to 4.10
Pharmacokinetic / Pharmacodynamic		7.1 to 7.2
Section	Listings	
ICH Listings	1 to 32	
Other Listings	33 to 55	

12.11.2. Mock Example Shell Referencing

Non IDSL specifications will be referenced as indicated and if required example mock-up displays provided in [Appendix 12: Example Mock Shells for Data Displays](#).

Section	Figure	Table	Listing
Study Population	POP_Fn	POP_Tn	POP_Ln
Pharmacodynamic and Biomarker	PD_Fn	PD_Tn	PD_Ln
Safety	SAFE_Fn	SAFE_Tn	SAFE_Ln
Pharmacokinetic	PK_Fn	PK_Tn	PK_Ln
Pharmacokinetic / Pharmacodynamic	PKPD_Fn	PKPD_Tn	PK/PD_Ln

NOTES:

- Non-Standard displays are indicated in the 'IDSL / Example Shell' or 'Programming Notes'.

12.11.3. Deliverables

Delivery [Priority] ^[1]	Description
IA1 [X]	Interim Analysis 1
IA2 [X]	Interim Analysis 2
HR [X]	Headline Results During Study (i.e. in-stream data review)
SAC [X]	Statistical Analysis Complete

NOTES:

1. Indicates priority (i.e. order) in which displays will be generated for the reporting effort

12.11.4. Study Population Tables

Study Population Tables					
No.	Population	IDSL / Example Shell	Title	Programming Notes	Deliverable [Priority]
Subject Disposition					
1.1.	All Subjects	ES1	Summary of Participant Disposition for the Participant Conclusion Record	ICH E3, FDAAA, EudraCT	SAC [1]
1.2.	All Subjects	SD1	Summary of Treatment Status and Reasons for Discontinuation of Study Treatment	ICH E3	SAC [1]
1.3.	Screened	ES6	Summary of Screening Status and Reasons for Screen Failure	Journal Requirements	SAC [1]
Protocol Deviation					
1.4.	All Subjects	DV1	Summary of Important Protocol Deviations	ICH E3	SAC [1]
Population Analysed					
1.5.	All Subjects	SP1	Summary of Study Populations	IDSL	SAC [1]
1.6.	All Subjects	SP2	Summary of Exclusions from the Evaluable Population	IDSL	SAC [1]
Demographic and Baseline Characteristics					
1.7.	All Subjects	DM1	Summary of Demographic Characteristics	ICH E3, FDAAA, EudraCT	SAC [1]
1.8.	All Subjects	DM11	Summary of Age Ranges	EudraCT	SAC [1]
1.9.	All Subjects	DM5	Summary of Race and Racial Combinations	ICH E3, FDA, FDAAA, EudraCT	SAC [1]
Prior and Concomitant Medications					
1.10.	All Subjects	MH1	Summary of Past Medical Conditions	ICH E3	SAC [1]

Study Population Tables					
No.	Population	IDSL / Example Shell	Title	Programming Notes	Deliverable [Priority]
1.11.	All Subjects	MH1	Summary of Current Medical Conditions	ICH E3	SAC [1]
1.12.	All Subjects	CM1	Summary of Concomitant Medications	ICH E3	SAC [1]
Exposure and Treatment Compliance					
1.13.	All Subjects	EX1	Summary of Exposure to Study Treatment	ICH E3 Exclude "Days on study drug" and "Daily Dose" from IDSL template.	SAC [1]

12.11.5. Pharmacodynamic and Biomarker Tables

Pharmacodynamic: Tables					
No.	Population	IDSL / Example Shell	Title	Programming Notes	Deliverable [Priority]
BAL Total Protein					
2.1.	Evaluable	PD_T1	Summary of BAL Total Protein by Timepoint (Baseline (2 h) and 26 h), Lung Lobe (LPS and Saline Challenge) and Treatment Group	Separate pages for arithmetic and geometric summary statistics.	IA1 [1], IA2 [1], HR [1], SAC [1]
2.2.	Evaluable	PD_T2	26 h BAL Total Protein: Summary of Posterior Distributions and Posterior Probability Statements from the Primary Analysis	Up to 4 pages. Page 1: Raw baseline values and baseline covariates values predictions are made at. Also add values used to determine predictions for any other covariates included in the model. Page 2: Adjusted posterior medians for each treatment group i.e. model adjusted predictions. 75% and 95% CrI. Page 3: Treatment comparisons in the form of adjusted posterior median absolute differences or percentage changes (dependent on endpoint and transformation). 75% and 95% CrI. Page 4: Posterior probability statements of interest.	IA [1], IA2 [1], HR [1], SAC [1]
2.3.	Evaluable	PD_T2	Sensitivity Analysis: 26 h BAL Total Protein including 26 h Saline Lobe BAL Total Protein as a Covariate: Summary of Posterior Distributions and Posterior Probability Statements from the Primary Analysis	Conditional output. See programming notes above.	SAC [1]

Pharmacodynamic: Tables					
No.	Population	IDSL / Example Shell	Title	Programming Notes	Deliverable [Priority]
2.4.	Evaluable	PD_T2	Sensitivity Analysis: 26h BAL Total Protein Excluding Participants with High Saline Lobe BAL Total Protein Level: Summary of Posterior Distributions and Posterior Probability Statements from the Primary Analysis	Conditional output. See programming notes above.	SAC [1]
2.5.	Evaluable	PD_T2	26 h BAL Total Protein and Total Neutrophil Count: Summary of Posterior Distributions and Posterior Probability Statements from the Multivariate Analysis	Conditional output. See programming notes above.	SAC [1]
BAL Total Neutrophil Count					
2.6.	Evaluable	PD_T1	Summary of BAL Total Neutrophil Count by Timepoint (Baseline (2 h) and 26 h), Lung Lobe (LPS and Saline Challenge) and Treatment Group	Separate pages for arithmetic and geometric summary statistics.	HR [1], SAC [1]
2.7.	Evaluable	PD_T2	26 h BAL Total Neutrophil Count: Summary of Posterior Distributions and Posterior Probability Statements from the Analysis	Up to 4 pages. Page 1: Raw baseline values and baseline covariates values predictions are made at. Also add values used to determine predictions for any other covariates included in the model. Page 2: Adjusted posterior medians for each treatment group i.e. model adjusted predictions. 75% and 95% CrI. Page 3: Treatment comparisons in the form of adjusted posterior median absolute differences or percentage changes (dependent on endpoint and transformation). 75% and 95% CrI. Page 4: Posterior probability statements of interest.	HR [1], SAC [1]

Pharmacodynamic: Tables					
No.	Population	IDSL / Example Shell	Title	Programming Notes	Deliverable [Priority]
BAL Differential Neutrophil Count					
2.8.	Evaluable	PD_T1	Summary of BAL Differential Neutrophil Count by Timepoint (Baseline (2 h) and 26 h), Lung Lobe (LPS and Saline Challenge) and Treatment Group	Separate pages for arithmetic and geometric summary statistics.	HR [1], SAC [1]
2.9.	Evaluable	PD_T2	26h BAL Differential Neutrophil Count: Summary of Posterior Distributions and Posterior Probability Statements from the Analysis	
Up to 4 pages.
 
Page 1: Raw baseline values and baseline covariates values predictions are made at. Also add values used to determine predictions for any other covariates included in the model.
 
Page 2: Adjusted posterior medians for each treatment group i.e. model adjusted predictions. 75% and 95% CrI.
 
Page 3: Treatment comparisons in the form of adjusted posterior median absolute differences or percentage changes (dependent on endpoint and transformation). 75% and 95% CrI.
 
Page 4: Posterior probability statements of interest.
	HR [1], SAC [1]
Exploratory BAL Biomarkers					
2.10.	Evaluable	PD_T1	Summary of Exploratory BAL Biomarkers (excluding WBCs) by Timepoint (Baseline (2h) and 26h), Lung Lobe (LPS and Saline Challenge) and Treatment Group	One page per analyte. Separate pages for arithmetic and geometric summary statistics.	SAC [1]

Pharmacodynamic: Tables					
No.	Population	IDSL / Example Shell	Title	Programming Notes	Deliverable [Priority]
2.11.	Evaluable	PD_T2	26h Exploratory BAL Biomarkers (excluding WBCs): Summary of Posterior Distributions and Posterior Probability Statements from the Analyses	Up to 4 pages per analyte. Page 1: Raw baseline values and baseline covariates values predictions are made at. Also add values used to determine predictions for any other covariates included in the model. Page 2: Adjusted posterior medians for each treatment group i.e. model adjusted predictions. 75% and 95% CrI. Page 3: Treatment comparisons in the form of adjusted posterior median absolute differences or percentage changes (dependent on endpoint and transformation). 75% and 95% CrI. Page 4: Posterior probability statements of interest.	SAC [1]
2.12.	Evaluable	PD_T1	Summary of BAL White Blood Cell Types (Totals and Differentials, except neutrophils): by Timepoint (Baseline (2h) and 26h), Lung Lobe (LPS and Saline Challenge) and Treatment Group	One page per analyte. Separate pages for arithmetic and geometric summary statistics.	SAC [1]

Pharmacodynamic: Tables					
No.	Population	IDSL / Example Shell	Title	Programming Notes	Deliverable [Priority]
2.13.	Evaluable	PD_T2	26h BAL White Blood Cell Types (Totals and Differentials, except Neutrophils): Summary of Posterior Distributions and Posterior Probability Statements from the Analyses	
Up to 4 pages per analyte.
 
Page 1: Raw baseline values and baseline covariates values predictions are made at. Also, add values used to determine predictions for any other covariates included in the model.
 
Page 2: Adjusted posterior medians for each treatment group i.e. model adjusted predictions. 75% and 95% CrI.
 
Page 3: Treatment comparisons in the form of adjusted posterior median absolute differences or percentage changes (dependent on endpoint and transformation). 75% and 95% CrI.
 
Page 4: Posterior probability statements of interest.
	SAC [1]
BAL Pharmacodynamic/Biomarker Corrected for Dilution Factor					
2.14.	Evaluable	PD_T1	Summary of All BAL Biomarkers Corrected for Dilution Factor by Timepoint (Baseline (2h) and 26h), Lung Lobe (LPS and Saline Challenge) and Treatment Group	Conditional output. One page per analyte. Separate pages for arithmetic and geometric summary statistics.	SAC [1]
2.15.	Evaluable	PD_T2	All BAL Biomarkers Corrected for Dilution Factor: Summary of Posterior Distributions and Posterior Probability Statements from the Analyses	Conditional output. See programming notes above.	SAC [1]
Exploratory Blood Biomarkers					
2.16.	Evaluable	PD_T1	Summary of Exploratory Blood Biomarkers by Timepoint and Treatment Group	Separate pages for arithmetic and geometric summary statistics.	SAC [1]

Pharmacodynamic: Tables					
No.	Population	IDSL / Example Shell	Title	Programming Notes	Deliverable [Priority]
2.17.	Evaluable	PD_T2	Exploratory Blood Biomarkers: Summary of Posterior Distributions and Posterior Probability Statements from the Analyses	
Approximately 7 pages per analyte. Add timepoint as first column.
 
Page 1: Raw baseline values and baseline covariates values predictions are made at. Also. add values used to determine predictions for any other covariates included in the model.
 
Page 2: Adjusted posterior medians at each timepoint i.e. model adjusted predictions. 75% and 95% CrI.
 
Page 3: Treatment comparisons in the form of adjusted posterior median absolute differences or percentage changes (dependent on transformation) for each timepoint. 75% and 95% CrI.
 
Page 4-7: Posterior probability statements of interest for '745 c.f. pbo – separate page for each timepoint.
	SAC [1]

